## **5. STUDY SUBJECTS**

### **5.1 Disposition of Subjects**

A table of frequency counts and percentages of all subjects who are screened, randomized, and in each analysis population will be provided. Subject disposition including study completion status and reasons for early termination will be tabulated by treatment group and overall. A by subject listing will be provided.

### **5.2 Protocol Deviations**

Distribution of the types of protocol deviations and the number of subjects that deviate from the protocol will be tabulated for the treatment groups in the ITT population. Protocol deviations will also be tabulated by severity (e.g., minor or major). A listing of all protocol deviations will be provided.

### **5.3 Demographic Characteristics**

Descriptive statistics will be used to summarize the demographic characteristics (age, gender, race, ethnicity, height, weight, and Body Mass Index [BMI]) for the ITT population. A by subject listing will be provided.

### **5.4 Baseline Characteristics**

Baseline characteristics of ITT subjects including historical SARS-CoV-2 results and pregnancy test will be listed and tabulated if appropriate.

### **5.5 Medical History**

All medical conditions will be classified by system organ class (SOC) and preferred term (PT) using the Medical Dictionary for Regulatory Activities (MedDRA). The number and percent of subjects with each medical condition will be presented for each SOC and PT for the ITT population.

## 5.6 Concomitant Medications

All concomitant medications collected will be coded using the World Health Organization (WHO) Drug Dictionary. The number and percent of ITT subjects using concomitant medications will be tabulated by Anatomical, Therapeutic, and Chemical (ATC) level 2 and by ATC level 4. If the ATC level 2 or 4 term is missing, the higher ATC level term will be used in the medication summary table and data listing.

Prior medications will be summarized separately from concomitant medications, for the overall ITT population.

Prior medications are defined as medications that ended prior to the date of randomization. Concomitant medications are defined as medications that started at any time but ended on or after the date of randomization, including those that are ongoing at study completion. In the case of a missing or partial end date/time, in order to determine whether a medication is prior or concomitant, the following conservative imputation rule will be used: the unknown portions of a medication end date/time will be imputed to the latest possible. The imputed medication end date/time will then be compared with the date of randomization to determine if the medication is prior or concomitant.

Note the imputed end date/time will only be used to determine whether a medication is prior or concomitant. The actual date/time reported on the electronic case report forms (eCRFs) will be presented in the listings.

All concomitant medications collected will be reviewed in a data review meeting conducted prior to database lock. ATC or Preferred terms for COVID-19 specific, potentially disease modifying medications will be identified by the study team. Subsequently, a tabular summary by treatment group of these COVID-19 specific concomitant medications based on the identified ATC terms will be generated. If clinically important imbalance was observed in the use of these medications between the 2 treatment groups, additional supplemental efficacy analyses may be performed in a post-hoc manner to adjust for the difference(s) in such medication use.

In addition, the daily fluid balance (intake and output) will be recorded while subjects are in hospital through Day 10. A sensitivity analysis on potential effects of fluid balance will be performed by using descriptive statistics.

## 6. EFFICACY ANALYSES

All efficacy analyses will be carried out using the ITT population. Data on all efficacy endpoints will be listed and tabulated if appropriate.

### 6.1 Primary Efficacy Endpoint and Analysis

The primary efficacy analysis will be carried out on the ITT population. If there is difference between the PP population and ITT population, the analysis will be repeated using the PP population.

The primary efficacy variable is all-cause mortality rate through Day 29. Subject status (Alive/Death) will be recorded in the database. If the vital status of the subject is missing, then the subject will be treated as death for the primary analysis.

The null hypothesis is that the all-cause mortality rate through Day 29 in subjects administered Gamunex-C plus SMT will be no different than the rate in subjects provided SMT alone;  $H_0: \pi_t - \pi_c = 0$ . The alternative hypothesis is that the all-cause mortality rate through Day 29 in subjects administered Gamunex-C plus SMT will be different than the rate in subjects provided SMT alone;  $H_1: \pi_t - \pi_c \neq 0$ .

The proportion of subjects who die within each treatment group will be presented along with a two-sided exact (Clopper-Pearson) 95% confidence interval (CI).

The observed difference in the mortality rate (proportion of deceased subjects) between treatment groups along with the exact unconditional 95% CI for risk difference will be calculated. The null hypothesis will be tested using Fisher's exact method and the p-value will be reported.

An alternative primary analysis will be performed in which the survival rates will be estimated using the Kaplan-Meier (KM) method. The KM estimates along with 95% CIs and survival curves will be provided. Based on the KM estimates, the survival probabilities and associated 95% CIs on Days 15 and 29 will be reported; in addition, the 25th, 50th (median), and 75th percentiles of the survival time with associated 95% CIs will be provided, as data permit. The survival rates between treatment groups will be compared using Log-rank test and the p-value from Log-rank test will be presented.

Subgroup analyses of the primary efficacy endpoint by baseline characteristics such as age group (with age cutoffs defined either by absolute values or by a summary metric [e.g., median] of the observed baseline values) and gender will be performed using the analysis method described above, if appropriate.

If for one or more subjects the actual treatment received is different from the randomized treatment and if deemed necessary, sensitivity analysis of the primary efficacy endpoint will be performed by repeating the primary efficacy analysis as described above in this section, but with subjects grouped according to the actual treatment received instead of the randomized treatment.

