## 2.2 Endpoints

### 2.2.1 Primary Efficacy Endpoint

The primary efficacy endpoint is all-cause mortality rate through Day 29.

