All subjects will be followed daily through Day 10. After Day 10, if subjects are discharged from the hospital, evaluations at Day 15 and 29 are required. Berlin criteria for ARDS and SOFA score will be assessed on Day 1, 5, 15, and 29. Subjects remaining hospitalized will be followed daily through Day 29. Phone Checks will occur at Day 60 and Day 90 for vital status (living or deceased), any hospital re-admissions or serious/non-serious AEs after the Day 29 Final Clinic Visit. See Appendix A for the Schedule of Events.

Clinical trial finalization will coincide with the last study visit of the last subject enrolled in the clinical trial. For an individual subject, end of study for the purposes of determining disposition and successful study completion is the Day 29/Final Clinic Visit performed at the scheduled on-study timeframe.

An overview of the study design is presented below:

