## 4. GENERAL CONSIDERATIONS FOR DATA ANALYSIS

Unless otherwise specified, continuous variables will be summarized using descriptive statistics (n, mean, standard deviation, median, minimum, and maximum). Categorical variables will be summarized showing the number and percentage of subjects within each category.

Summary results will be provided for each treatment group. All tabulations will be based on pooled data across centers.

All statistical tests will be two-sided and tested at the 5% level of significance.

Analyses will be performed using SAS for Windows statistical software, version 9.4 or higher (SAS, Cary, NC), except where other software may be deemed more appropriate. In the event that other software is used to perform some analyses, the details will be provided in the Clinical Study Report.

■ will perform all efficacy and safety analyses described in this SAP.

Subject data will be listed, sorted by treatment group and subject number. When applicable, listings will be additionally sorted by visit and assessment date/time.

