#### **4.4 Handling of Dropouts or Missing Data**

Missing data will be treated as missing and no method for imputation is planned for study population or safety analyses except for the partial end dates/times for concomitant medications (Section 5.6) and partial onset dates/times for AEs (Section 7.2.1). When applicable, missing data for binary and selected continuous efficacy endpoints will be imputed using a most conservative/worst case approach, and the related details are described in Section 6.

Time to event endpoints will have events coded as right censored or competing events per the

following table:

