### **9. SAMPLE SIZE AND POWER CALCULATIONS**

Because of the urgency and lack of previous prospective COVID-19 data, sample size estimation remains incompletely defined; however the size of this pilot study is commensurate with other Phase 2 investigations ongoing during the COVID-19 pandemic. Approximately 100 subjects are allowed to be randomized as part of a humanitarian effort against COVID-19.

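### Counting missing vital status as death in both arms is worst case for each arm's mortality but not for the treatment difference; the SAP should define Day 29 status from later contacts and add sensitivity analyses that test the comparison

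*SAP*

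**What the plan says.** The endpoint is binary (SAP 2.2.1): "The primary efficacy endpoint is all-cause mortality rate through Day 29". SAP 6.1 sets a null hypothesis of no difference between the arms, against a two-sided alternative. On the test it says: "The null hypothesis will be tested using Fisher's exact method". SAP 4 adds: "All statistical tests will be two-sided and tested at the 5% level of significance".

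For unknown outcomes SAP 6.1 says: "If the vital status of the subject is missing, then the subject will be treated as death for the primary analysis". It does not distinguish the arms. SAP 4.4 describes the general approach in these words: "missing data for binary and selected continuous efficacy endpoints will be imputed using a most conservative/worst case approach".

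Three other provisions matter:

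- SAP 6.1 also plans a Kaplan-Meier and log-rank analysis as an alternative primary analysis. Table 1 in SAP 4.4 censors subjects at the last contact when they were known to be alive.
- The only analysis of the primary endpoint that SAP 6.1 calls a sensitivity analysis regroups subjects by treatment actually received. It leaves the missing-data rule unchanged.
- Vital status is collected again by phone at Days 60 and 90 (SAP 3.1, protocol 7.2.8). SAP 6.1 does not say how those calls bear on Day 29 status.

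The trial is open-label, randomised 1:1, with about 100 subjects.

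**The concern.** A single-arm mortality rate is highest when every unknown subject is counted as dead, so for that quantity the rule is a true worst case. The trial tests a difference, and adding deaths to both arms can move a difference either way. The worst case for a claim that IVIG reduces mortality would count unknown IVIG subjects as dead and unknown SMT-alone subjects as alive. The plan's rule does the second half the other way round.

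An open-label design does not itself create unequal follow-up. It does make it more plausible, because subjects know which treatment they received. SMT-alone subjects may lose interest; IVIG subjects may withdraw after adverse events. The imputed deaths enter the proportions, the risk difference, its confidence interval and the Fisher p-value. At about 50 per arm, a handful of subjects can decide whether p falls below 0.05.

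**Working it through.** **Inputs from the documents.** About 50 per arm follows from "Approximately 100 subjects are allowed to be randomized as part of a humanitarian effort against COVID-19" and 1:1 allocation. The test is two-sided Fisher at 0.05. The plan has no power figure to reproduce, since SAP 9 says that "sample size estimation remains incompletely defined". It gives no mortality or dropout rate either.

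**Assumptions.** Mortality and missingness rates are mine, shown as ranges.

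**Bias.** For one arm let p be true mortality, m the fraction with unknown status and q the true death risk among them. The analysed rate is p + m(1 − q). The bias in the difference (IVIG minus SMT alone) is

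m_T(1 − q_T) − m_C(1 − q_C).

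With equal m and equal q it is zero under the null. If q is similar in the two arms, the bias favours the arm with less missingness. If a share s of survivors is unknown, the analysed rate is p + (1 − p)s.

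**No true effect.** Take p = 0.30 in both arms, so about 50 × 0.70 = 35 survivors per arm. Rejection rates come from exact enumeration of two Binomial(50) arms.

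| s, IVIG | s, SMT | SMT survivors unknown (35 × s) | Analysed rates | Bias, points | Fisher rejection |
|---|---|---|---|---|---|
| 0 | 0 | 0 | 30.0% v 30.0% | 0 | 3.1% |
| 0 | 5% | 1.75 | 30.0% v 33.5% | −3.5 | 4.2% |
| 0 | 6% | 2.1 | 30.0% v 34.2% | −4.2 | 4.7% |
| 0 | 10% | 3.5 | 30.0% v 37.0% | −7.0 | 7.8% |
| 0 | 15% | 5.25 | 30.0% v 40.5% | −10.5 | 14.3% |
| 5% | 10% | 3.5 | 33.5% v 37.0% | −3.5 | 4.2% |

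Example: 0.30 + 0.70 × 0.10 = 0.37. Swapping the arms gives the same rejection rates, now favouring SMT alone.

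**Other mortality levels.** With 10% of SMT survivors and no IVIG survivors unknown, rejection goes from 2.8% to 10.9% at 20% mortality, and from 3.2% to 6.7% at 40%.

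**Sicker missing subjects.** With 10% of the whole SMT arm unknown, none on IVIG and p = 0.30, the bias is −10 points and rejection 13.2% if all the unknown are alive (q = 0). At q = 0.60 these are −4 points and 4.6%.

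**True effect, equal missingness.** Take 20% v 40% with 10% of survivors unknown in each arm. The analysed rates are 0.20 + 0.80 × 0.10 = 0.28 and 0.40 + 0.60 × 0.10 = 0.46. The difference shrinks from 20 to 18 points and power falls from 52% to 39%.

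**Single data sets.**

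| Known deaths, IVIG v SMT | p, unknown SMT counted alive | Unknown SMT subjects | p, unknown SMT counted dead |
|---|---|---|---|
| 8/50 v 15/50 | 0.153 | 3 | 0.039 (8 v 18) |
| 10/50 v 15/50 | 0.356 | 5 | 0.049 (10 v 20) |

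No IVIG subject is unknown here, so the third column is the true worst case for IVIG. In both rows the plan's rule is less conservative than that.

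**The case against.** The strongest reply is that the problem will seldom arise. Subjects still in hospital are assessed daily through Day 29 (protocol 4.2). The Day 29 visit can take place at home or at a local site, with a phone call as fallback (protocol 7.2.7). Withdrawn subjects are asked back for Day 29 unless consent is withdrawn (protocol 5.3.4), and two more calls follow. Fisher's test is itself conservative at this size, so mild imbalance leaves the error rate below 5%. The study is an exploratory pilot with no stated power, the rule is prespecified and identical in both arms, and a censored Kaplan-Meier analysis is already planned.

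Most of that stands, and it limits the size of the point. It does not make the rule conservative for a difference. Withdrawal of consent and loss to follow-up (a listed reason in protocol 5.3.2) can still leave status unknown. The Kaplan-Meier analysis does not alter the Fisher result, and it assumes non-informative censoring, which is doubtful for ICU withdrawals.

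Three stronger readings are tempting and are not supported:

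- **That the rule necessarily biases the trial, or biases it towards IVIG.** Under the null it needs unequal missingness or unequal risk among the missing, and the documents give no ground for predicting either.
- **That a subject found alive at Day 60 or 90 would be analysed as dead at Day 29.** SAP 6.1 applies the rule only when vital status is missing and is silent on the later calls. Silence is a gap in the definition, not an exclusion.
- **That Kaplan-Meier must replace Fisher as the primary analysis.** Protocol 9.1 names Fisher's exact or the chi-square test, so the change would depart from the protocol and exchange one untestable assumption for another.

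**Conclusion.** The point holds in a limited form. Missing counted as death bounds each arm's mortality from above but is not a worst case for the comparison, so SAP 4.4's description is wrong for the hypothesis being tested. No planned analysis tests the primary result under an arm-specific worst case.

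The size depends on rates that the documents do not give. At 50 per arm and 30% mortality, the error rate first passes 5% between 6% and 10% of SMT survivors unknown with none on IVIG, which is roughly three or more subjects. The threshold is somewhat lower at 20% mortality and higher at 40%. If the unknown subjects are mostly truly dead, the bias is smaller. The planned follow-up should keep the numbers down, so this is a safeguard worth adding rather than evidence that the primary analysis is invalid.

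**What to change.** Keep Fisher's exact test as the primary analysis, and change the SAP as follows:

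1. In 6.1, state that a subject known to be alive at any contact on or after Day 29, including the Day 60 and Day 90 calls, is alive at Day 29. Missing counted as death then applies only to subjects still unknown.
2. In 4.4, stop describing the rule as the most conservative for the between-arm comparison.
3. Report the number with unknown Day 29 status by arm.
4. Add a sensitivity analysis with the true worst case for IVIG: unknown IVIG subjects dead, unknown SMT-alone subjects alive.
5. Add a tipping-point table over the possible numbers of deaths among the unknown in each arm.
6. Present these beside the planned Kaplan-Meier analysis, and state its assumption of non-informative censoring.

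The cost is a SAP wording change and a few extra tables; no new data are needed. The drawback for the sponsor is that a significant result may be shown to be less robust than its p-value suggests.

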2.3.2 Risks

Full details regarding tolerability and safety of Gamunex-C are provided in the prescribing information and the IB. The main risks of Gamunex-C are summarized below:

- Gamunex-C is contraindicated in subjects with a known history of anaphylactic or severe systemic reaction to human immunoglobulins, especially in subjects with antibodies against IgA.

GRIFOLS	Number	BLG-CL-PRT-000020	Version	4.0	Status	Effective	Effective Date	19-Jul-2021
	GC2007 - A Multicenter, Randomized, Open-label Parallel Group Pilot Study to Evaluate Safety and Efficacy of High Dose Intravenous Immune Globulin (IVIG) plus Standard Medical Treatment (SMT) versus SMT alone in Bioscience Industrial Group						Page	25 of 91

- Certain adverse events may be related to the rate of infusion. Subjects must be closely monitored and carefully observed for any symptoms throughout the infusion period.
- There is clinical evidence of an association between IVIG administration and thromboembolic events such as myocardial infarction, cerebral vascular accident (including stroke), PE, and DVT that is assumed to be related to a relative increase in blood viscosity through the high influx of immunoglobulin in at-risk subjects. In subjects at risk for thromboembolic ARs, IVIG products should be administered at the minimum rate of infusion and dose practicable.
- Cases of acute renal failure have been reported in subjects receiving IVIG therapy. In most cases, risk factors have been identified, such as pre-existing renal insufficiency, diabetes mellitus, hypovolemia, overweight, concomitant nephrotoxic medicinal products, or age over 65. In subjects at risk for acute renal failure, IVIG products should be administered at the minimum rate of infusion and dose practicable.
- Aseptic meningitis syndrome (AMS) has been reported to occur in association with IVIG treatment. Discontinuation of IVIG treatment has resulted in remission of AMS within several days without sequelae.
- Gamunex-C may contain blood group antibodies which may act as hemolysins and induce in vivo coating of red blood cells with immunoglobulin, causing a positive direct antiglobulin reaction (Coombs test) and, rarely, hemolysis. Hemolytic anemia can develop subsequent to IVIG therapy due to enhanced red blood cells sequestration. IVIG recipients should be monitored for clinical signs and symptoms of hemolysis. If these are present after IVIG infusion, perform appropriate confirmatory laboratory testing.

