#### 4.5 Multiple Comparisons

Because of the exploratory nature of this study, there will be no adjustment for multiple comparisons.

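### SAP 6.1 tests mortality separately within age and gender subgroups, plans no treatment-by-subgroup comparison and leaves the age cut open, so a false 'works in one subgroup only' pattern can readily arise

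*SAP*

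**What the plan says.** SAP 6.1 tests Day 29 all-cause mortality by Fisher's test, where the "exact method and the p-value will be reported", together with the risk difference and its exact unconditional 95% CI. An alternative Kaplan-Meier analysis follows: "The survival rates between treatment groups will be compared using Log-rank test and the p-value from Log-rank test will be presented".

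Subgroup analyses by age group and gender, given as examples of baseline characteristics, "will be performed using the analysis method described above, if appropriate". Age groups are formed "with age cutoffs defined either by absolute values or by a summary metric" of the baseline ages observed, the median being the example given.

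Two general rules apply. SAP section 4 says: "All statistical tests will be two-sided and tested at the 5% level of significance". SAP 4.5 says that "there will be no adjustment for multiple comparisons", because the study is exploratory.

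Neither document plans a treatment-by-subgroup interaction. Elsewhere in the SAP, age and gender appear only as main-effect covariates, fixed in the mixed models and optional in the ANCOVA and ordinal models. Protocol section 9.1 plans no age or gender subgroup analysis.

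**The concern.** A subgroup analysis asks whether the treatment effect differs between groups. Separate tests within each group do not answer that. With about 100 subjects in total, each stratum has little power. When two underpowered tests address the same true effect, one may cross 0.05 and the other miss it by chance alone.

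The open age cut adds to this. No value, selection rule or deadline is stated. The trial is open-label, and the interim safety analysis in SAP section 8 uses the section 7 summaries, which tabulate adverse events leading to death by arm. Nothing in the plan keeps the choice of cut separate from outcome by arm.

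At stake is interpretation. A pilot's subgroup table is a natural place to look when choosing the population of a later trial, and a pattern produced by noise could narrow that population wrongly.

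**Working it through.** **Inputs from the documents.** About 100 subjects randomized 1:1, so about 50 per arm. Two-sided 5%, no multiplicity adjustment. Fisher's test, with log-rank as the alternative. No control mortality, effect size or power is stated, so there is no figure of the plan's own to reproduce.

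**Assumptions.** Two equal strata of 25 v 25, and the same true mortality in both. For the simulations: age normal with mean 60 and SD 13, 35% of subjects in one gender, and no true interaction.

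**Step 1. Same effect in both strata.** Let p be the exact Fisher power at 25 v 25, found by enumerating both binomials. The two strata are independent, so:

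- exactly one significant = 2p(1 − p)
- neither significant = (1 − p)²

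| Mortality, control v treated | p | Exactly one | Neither |
|---|---|---|---|
| 40% v 30% | 7.0% | 2 × 0.070 × 0.930 = 13% | 0.930² = 87% |
| 40% v 20% | 23.1% | 2 × 0.231 × 0.769 = 36% | 0.769² = 59% |
| 40% v 15% | 38.3% | 2 × 0.383 × 0.617 = 47% | 0.617² = 38% |

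For scale, Fisher power in the whole trial (50 per arm) at 40% v 20% is 52%. A real median split would not give exactly 25 v 25. Allowing for that, simulation puts the 36% at about 40%. The chance of a discordant pair for age or gender, with the median age cut, is then about 56%.

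**Step 2. No true effect.** Four independent tests at a true 5% would give 1 − 0.95⁴ = 18.5%. Fisher's test is conservative here: its actual size at 25 per arm is 2.2% to 3.3% for mortality of 20% to 50%. Simulation (2,000 trials at each of 20%, 30% and 40% mortality) gives, for at least one significant subgroup:

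- Fisher only, median age cut plus gender: about 11%
- Fisher only, age cut free among the median, 50, 60, 65 and 70: about 19%
- Fisher or log-rank, median cut: 16% to 17%
- Fisher or log-rank, five cuts: 27% to 28%

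A separate run (3,000 trials, 35% mortality, with 55 added as a sixth cut) gave 21% for Fisher only, so about 20% is a fair summary for a free choice of cut. By symmetry, about half of these results would favour treatment.

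**Step 3. The interaction instead.** In the same simulations, a Wald test on the difference between the two risk differences (median age split) was significant in 4.9% to 5.6% of trials, with or without a uniform treatment effect. For two pre-specified factors the rate is at most about 1 − 0.95² = 9.75%.

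Its power is low. Suppose mortality is 40% v 20% in one half and 40% v 40% in the other:

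- variance = (0.4×0.6 + 0.2×0.8)/25 + (0.4×0.6 + 0.4×0.6)/25 = 0.0160 + 0.0192 = 0.0352
- SE = √0.0352 = 0.188
- z = 0.20/0.188 = 1.07, so power is about 19%

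**The case against.** The best defence is context. This is a pilot declared exploratory, the subgroup analyses are optional and supplementary, and the SAP does not say that any subgroup claim will be made. The subgroup risk differences with 95% CIs are already planned, because the method being repeated includes them. The interaction test would seldom find a real difference. All of this stands, and it limits the weight of the point. It does not make within-subgroup p-values answer a question about differences between subgroups. The exploratory label is the SAP's reason for not adjusting for multiplicity, which is a separate matter.

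Three stronger readings are tempting, and the documents do not support them.

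- **A reader might infer that a false subgroup finding will arise, or that discordant strata are the usual result.** At 40% v 20% the most frequent outcome is that neither stratum is significant (59%). At 40% v 30% discordance falls to 13%. The 36% and 47% figures rest on mortality being halved or better.
- **A reader might infer that the age cut is to be taken from the outcome data.** The only summary metric named is the median of observed baseline ages, which does not depend on outcome. The gap is the unfixed choice between that and an unstated absolute value. The rise to about 20% under no effect requires someone to search across cuts.
- **A reader might infer that the protocol supplies 65 years as the natural cut.** The phrase in Protocol 2.3.2, "overweight, concomitant nephrotoxic medicinal products, or age over 65", lists risk factors for acute renal failure with IVIG. It is not a cut for COVID-19 mortality or for treatment effect.

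**Conclusion.** The point holds as a weakness of method and interpretation. The planned subgroup tests cannot show whether the effect differs by age or gender, and the open age cut adds avoidable freedom. The chance of a misleading discordant pair in a single two-way split is about 13% to 47% over the uniform effects tried. With no effect, the chance of any significant subgroup by Fisher is about 11% for one fixed cut and about 20% for a free choice of cut. Counting the log-rank p-value as well raises both null figures.

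Every mortality rate, the age distribution, the gender split and the alternative cuts are assumptions, because the documents give none. The absence of an interaction analysis and of a fixed cut does not depend on them. The primary ITT comparison is not affected.

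**What to change.** In SAP 6.1, before database lock and without reference to outcome by arm:

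1. Fix one age rule, for example the observed baseline median or one stated absolute value.
2. Keep the planned subgroup risk differences with 95% CIs.
3. Add, for age and for gender, the difference between the subgroup risk differences (treatment-by-subgroup interaction) with 95% CI and p-value.
4. State that subgroup differences are judged on that interaction, not on within-subgroup p-values, and that the results are descriptive.

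The cost is a few lines of SAP text and a little more analysis, with no new data. Because of its low power (Step 3), the interaction test guards against false subgroup claims but will rarely detect a true difference. Its CI should therefore be read alongside the p-value.
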